Post-Release Telephone Sessions. The same clinician who met with the individual in jail will contact him or her 4 times by phone at key time points (within the first week, 1 month, 3 months, and 6 months) after jail release, providing the most frequent contact in the highest risk period just after release. For individuals in crisis, clinicians have the option of scheduling an additional 4 calls. Calls are structured and have an agenda: (1) mood check and suicide risk assessment; (2) review and revise the safety plan; and (3) review treatment options and problem-solve obstacles to treatment. Clinicians ask when the person's next mental health appointment is scheduled, assess motivational and structural barriers to attendance, and help address these barriers. Clinicians can help identify treatment and other resources and facilitate appointments for patients if needed. If patients are assessed to be at acute risk, we will take appropriate action to maintain their safety, which may include contacting existing providers, ED referral, or calling the police (see Human Subjects).

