more difficult calls, to provide support and information to participants, and to access local service referrals as appropriate. If needed, actions that may be taken include having a designated family member or friend transport the person to the closest hospital, or sending local police to escort the person to the nearest hospital to be evaluated for inpatient psychiatric stabilization. If a call is disconnected during this "warm transfer," the Boys Town mental health crisis counselor will use the contact information provided in an attempt to re-contact the participant, up to 3 separate times. If, after 3 attempts, the mental health crisis counselor is unable to contact the participant, local police will be contacted and dispatched to perform a wellness check. Based upon experience in the ED-SAFE study using a similar protocol in collaboration with Boys Town, we anticipate that this latter scenario will occur very infrequently. Within 24 hours of each Boys Town contact, a pdf Call Record will be provided via encrypted email with information regarding the disposition and outcome of each call, for purposes of AE/SAE event monitoring and reporting, and for purposes of data collection (e.g., if a participant was transferred to the Emergency Department) and participant tracking.

It is likely that most suicidal behavior detected during the follow-up assessment will be historical, and therefore will not require a transfer of the call between the blind evaluator and Boys Town. However, for any emergent suicidal ideation or behavior (i.e., any suicide behavior in the past week; C-SSRS = yes to suicide attempt, aborted attempt, interrupted attempt, or preparatory behavior), the blind evaluator will follow the specific protocol for mandatory transfer of calls to Boys Town, as described above. For any emergent, but recent (i.e., since the last assessment, but not including the past week) suicidal behavior, the blind evaluator will offer to transfer the participant to the Boys Town mental health crisis counselor for additional consultation and referral; this transfer will be voluntary for such participants. In addition to evaluator training on all related protocols, the REDCap database will be programmed to generate prompts, driven by entered assessment data, to further guide the decision making process of blind evaluators with respect to transfer of calls to Boys Town.

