#### 9. Outcome Measures

Assessments will take place at baseline, and at 4, 16, 34, and 52 weeks post-release. Baseline assessments (including informed consent, locator, and release of information paperwork) will take place in person at the jail; RAs will offer to read each study assessment aloud. Follow-up assessments will take place by telephone (the most feasible way to do follow-ups with this population), unless a participant is reincarcerated, in which case the follow-up assessment will take place in person at the jail/prison. If a participant is in a residential treatment facility, the follow-up assessment may take place by phone or in person at the residential treatment facility.

Table C1: Assessments	Туре	Time (min)	Baseline	4, 16, 34, and 52 week Follow-up
Suicidal Ideation and Behavior				
Columbia Suicide Severity Rating Scale (C-SSRS) 181	Interview	20	X	X
L.I.F.E. 182 – suicidal ideation and behavior	Interview	10		X
Suicide deaths: record review (state/national death registry)	Objective	0		X
Hospitalizations: Tx History Interview, record review (local hospitals)	Objective	0	X	X
Psychiatric Symptoms:				
DSM-5 Cross-Cutting Measure	Self-Report	7	X	X
K6	Self-Report	1	X	X
LEC/PCL	Self-Report	7	X	X
AUDIT and DUDIT	Self-report	7	X	X
Overdose	Self-report	10	X	X
Functioning: VR-12  from RAND Medical Outcomes Study	Self-Report	3	X	X
Hypothesized Mechanisms				
Treatment utilization: Treatment History Interview 	Interview	8	X	X
Belongingness: Interpersonal Needs Questionnaire-12 	Self-Report	5	X	16 ,34, 52 only
Suicide-related problem-solving: Suicide Related Coping Measure	Self-Report	5	X	16, 34, 52 only
Diagnosis: Mini International Neuropsychiatric Interview (MINI)  : lifetime psychosis, mania/hypomania, major depressive episode	Interview	10		4 week only
Safety Plan use in the context of Substance Abuse	Interview	10		52 only
Total patient time for interview (min)			Consent[contact]

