Primary outcome. Suicide Events is a composite score consisting of the total number of occurrences of any of the following in the year after jail release: (a) attempted suicide (includes suicide deaths), (b) suicide behaviors (preparatory acts, aborted or interrupted suicide attempts), as defined using the Columbia criteria, 181,188 and (c) suicide-related hospitalizations. We will use the Treatment History Interview (THI189) as well as hospital records to track the number of subsequent hospitalizations and reasons for these admissions. Suicide event data will be assessed using data collected from all possible sources, including follow-up assessments (C-SSRS, THI), (b) hospital chart reviews, and (c) state/national registries. Data from all sources will be reviewed by 2 research team members for congruence. Disagreements will be reviewed and adjudicated by ... All reports will be classified using C-SSRS criteria. The C-SSRS is the recommended measure of suicidal ideation and behaviors in the NIH PhenX Toolkit as a core data element in all clinical trials for suicide prevention. Although it will not be included in our suicide event composite, we will also track implementation of rescue procedures (e.g. calling Emergency Services/police, breaking confidentiality to inform clinician of high suicide risk) during SPI phone calls or study assessments and compare conditions on this variable.

**Secondary outcomes.** Suicide Attempts. We will separately assess and evaluate total number of subsequent attempts using the procedures described above. Weeks of active suicidal ideation during the follow-up period will be operationalized using the Longitudinal Interval Follow-

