Hypothesized mechanisms of SPI effects. We define treatment utilization (primary) as the number of outpatient mental health and substance use visits attended in the community in the 3 months prior to baseline or since the last assessment, as indexed by the THI. Belongingness (exploratory) will be assessed using the Interpersonal Needs Questionnaire (INQ-12). 185,193 Suicide-related problem-solving (exploratory) will be assessed using a standard checklist of suicide safety behaviors and asking whether each was utilized during the most suicidal period since the last interview (identified on the C-SSRS). The checklist includes two subscales to minimize assessment reactivity: the sum of the number of recommended (e.g., call a friend) and the sum of the number of not recommended (e.g., use drugs) responses to suicidal thoughts or urges. These are the most direct, objective measures possible given the time-pressed, chaotic jail setting for baseline assessments and telephone follow-up.

Additional outcomes. Suicide deaths. Given the low incidence of suicide deaths, even in this high risk sample, we do not expect to have sufficient numbers of suicide deaths (separate from the suicide event composite) for meaningful analyses. However, we will track number of suicide deaths using all possible data sources, including hospital records and reviews of state and national death registries. Although our intervention does not target re-arrest directly, it is possible that by increasing service linkage, SPI could reduce re-arrest; therefore, we will assess number of re-arrests and compare conditions on this variable. We will also track days incarcerated in the year after the index release to weight participants by time in the community for other analyses. In addition, a brief questionnaire was added to the end of the study to collect open-ended participant feedback about his/her experience in the study.

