**Mechanisms of intervention effects.** We will separately test the hypotheses that, relative to SOC alone, SPI + SOC will result in more treatment utilization (number of outpatient mental health and substance use visits as assessed by the THI), more sense of belongingness (INQ-12 Belongingness Scale score), and better suicide-related problem solving (as assessed by the safety behavior checklist), our proposed primary and exploratory mechanisms, using Mplus, which can accommodate both standard and Poisson-class regression methods. We will then test the hypothesis that treatment utilization, suicide-related problem-solving skills, and belongingness (1) predict suicide events, and (2) mediate the effects of SPI on suicide events in a structural equation model framework to decompose total effects into direct and specific indirect effects. As recommended by MacKinnon et al, the statistical significance of the indirect effect will be assessed using bias-corrected bootstrapped standard errors; 95% CI estimates will be provided.

**Predictors/Personalization**. We will explore gender, race/ethnicity, lifetime suicide attempts, lifetime highest C-SSRS SI intensity score, severe mental illness (schizophrenia, bipolar disorder), substance use, and # of lifetime arrests as moderators. We expect that SPI is appropriate for a full range of at-risk jail detainees.

Cost-effectiveness analyses. We propose a comparative cost effectiveness (CE) analysis of SPI + SOC relative to SOC. The primary effectiveness measure is the sum of suicide-related hospitalizations and medically treated and fatal suicide acts, with a secondary measure of QALYs (see D2.12). Following widely accepted CE analysis guidelines, analyses will adopt a societal perspective, considering all economic costs regardless of source. If direct cost savings exceed the program costs, the program is said to offer net cost savings. We describe our statistical plan for determining mean change in and standard deviations of these measures above. The CE ratio equals  $\Delta C/\Delta E$ , where  $\Delta C$  is the difference in costs between SPI + SOC and SOC alone and  $\Delta E$  is the difference in the outcome measure. Using the Crystal Ball add-in to Excel, we will bootstrap 95% confidence intervals around the CE ratio and calculate a cost-effectiveness acceptability curve. Sensitivity analysis will examine CE ratios at 0%, 1% and 5% discount rates.

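### The mediation plan fixes no time order between mediators and the year-long event count, so reverse causation can bias the indirect effect, for treatment utilization possibly to the wrong sign

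*Combined protocol and SAP*

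**What the plan says.** **Outcome.** Section 9 defines the outcome over the whole year: "Suicide Events is a composite score consisting of the total number of occurrences of any of the following in the year after jail release". Section 10A tests it over the 52-week follow-up.

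**Schedule.** "Assessments will take place at baseline, and at 4, 16, 34, and 52 weeks post-release". Table C1 collects treatment utilization at all four follow-ups. Belongingness (INQ-12) and suicide-related coping are collected at baseline and then only at weeks 16, 34 and 52.

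**Mediators.** Treatment utilization, named the primary mechanism, is a count: "number of outpatient mental health and substance use visits attended in the community in the 3 months prior to baseline or since the last assessment". The coping checklist works by "asking whether each was utilized during the most suicidal period since the last interview". Belongingness and coping are labelled exploratory.

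**Model.** Section 10A first compares the arms on each mediator. It then tests whether the mediators predict suicide events and "mediate the effects of SPI on suicide events in a structural equation model framework", with direct and specific indirect effects and bootstrapped intervals. It names no mediator wave, lag, landmark or split of the outcome year, and no sensitivity analysis for reverse causation. Adjustment for baseline levels of dependent variables is stated for analyses generally.

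**Route from event to care.** Under section 8C, when suicidal behaviour since the last assessment (but not in the past week) is reported, "the blind evaluator will offer to transfer the participant to the Boys Town mental health crisis counselor for additional consultation and referral". Section 10B adds that participants who report significant suicide risk are referred to further care.

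**The concern.** A mediator has to come before the outcome it explains. Here visits and events accrue in the same intervals, and the protocol itself sends people toward care after suicidal behaviour. Someone with an event may then attend more outpatient visits because of it. If visits and events are related without regard to order, visits that protect can look harmful, and visits that do nothing can look predictive.

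The feedback may also differ by arm. Section 1H lets SPI clinicians schedule four extra calls for people in crisis, and the call agenda covers treatment options and obstacles to treatment.

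The coping checklist is tied to suicidality by construction, because it records what was done in the worst period. Belongingness and coping have no post-baseline value before week 16. By then the time just after release has passed, which section 1H singles out when it describes the calls as "providing the most frequent contact in the highest risk period just after release".

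At stake is the mechanism aim: whether SPI works through linkage to treatment. Section 10B claims enough power for any clinically important mediation effect, but power does not protect against a biased path. A larger sample only makes a wrong sign more significant.

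**Working it through.** **1. The plan's own mediation figure.** Inputs from section 10B: 78% of 800 = 624 evaluable, alpha 0.05, and arm-mediator correlation r from 0.2 to 0.5. Two-sided testing is from section 10A. Power of 80% is stated for the main effect and assumed here for mediation. The standardised detectable path is (1.960 + 0.842) / sqrt(N(1 - r²)).
- r = 0.2: 2.802 / sqrt(624 × 0.96) = 0.1145
- r = 0.5: 2.802 / sqrt(624 × 0.75) = 0.1295

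These round to the stated 0.11 and 0.13, so the figure is reproduced. The formula contains no time order.

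**2. Timing.** Outcome: weeks 0-52. Visits: weeks 0-4, 4-16, 16-34 and 34-52, the same intervals. Belongingness and coping: first post-baseline value at week 16, after 16/52 = 31% of the outcome year. Baseline adjustment does not order anything after release.

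**3. When the sign flips.** Let M be visits without feedback, Y the event count, β the size of the protective standardised slope within arm, and d the visits added per event. Observed visits are M + dY, so

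cov(M + dY, Y) = -β·SD(M)·SD(Y) + d·SD(Y)².

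This turns positive once d exceeds β·SD(M)/SD(Y). Section 10B gives event rates of 10/18/12% (SOC) and 5.5/9/7% (SPI) with correlation 0.50. The pooled within-arm SD(Y) is then 0.64 if the correlation is latent and 0.73 if it is between the observed outcomes; 0.68 is used. The visit SD is not in the documents and is assumed. With β = 0.1295, the plan's largest detectable value:

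| Assumed visit SD | Visits per event at which the sign flips |
|---|---|
| 5 | 0.1295 × 5 / 0.68 = 0.95 |
| 10 | 0.1295 × 10 / 0.68 = 1.9 |
| 20 | 0.1295 × 20 / 0.68 = 3.8 |

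**4. Simulation of same-year totals.** N = 624; control event rate 0.40 a year (10% + 18% + 12%). Assumptions not in the documents: 6 to 12 visits a year with skewed variation between people, variation in underlying risk, and each visit lowering the event rate by 5%. Share of trials with the wrong sign on the visits-to-events path:

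| Visits added per event | 0 | 0.5 | 1 | 2 | 4 |
|---|---|---|---|---|---|
| Baseline visits in model, 6-12 visits/year | 14-18% | 42-70% | 74-98% | 98-100% | 100% |
| Baseline visits not in model, 6 visits/year | 11% | 38% | 69% | 98% | not run |
| Baseline visits not in model, 12 visits/year | 2% | 8% | 12% | 47% | 97% |

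The rows differ mainly because adjusting for baseline visits removes stable differences between people and leaves the event-driven part of the visit count dominant. Rerunning the design with and without that covariate gives the same pattern. A wrong sign is less often a significant one: without baseline visits, it was significant in 7% (1 added visit) and 53% (2) of trials at 6 visits a year, and in 2% (2) and 28% (4) at 12.

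A separate linear simulation (visit SD 10, slope near 0.13) gave the wrong sign in 0%, 10%, 64%, 99% and 100% of trials for 0, 1, 2, 3 and 4 added visits.

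**5. With time order imposed.** A week-16 landmark needs the week-16 interview: 800 × 0.92 × 0.80 = 589. The formula in step 1 then gives 0.118 to 0.133. If events are spread evenly, 36/52 = 69% stay in the outcome. The formula reflects only the smaller N, so it understates the loss. In simulation, a week-16 lagged model adjusted for baseline visits and early events was unaffected by added visits and gave 2-8% false positives, but its power was only about 15-38%. When higher-risk people attended more care, false positives rose to about 18% in one scenario.

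**The case against.** The strongest reply is that section 10A is silent rather than wrong. A structural equation model can be lagged, Table C1 collects the mediators serially, and values at weeks 4, 16 and 34 precede later events. A reader might infer that the plan correlates same-year totals, or that the data cannot support an ordered analysis. The documents support neither inference. The simulation shows what one permitted reading would do, not what the plan commits to.

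A reader might also infer that all three mediators would take the wrong sign. That does not follow. If events lower belongingness, the bias runs in the hypothesised direction and exaggerates mediation. For recommended coping behaviours a wrong sign is plausible, but only visits were simulated.

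The size rests on assumptions. The documents give a route from event to care, but no visits per event and no visit SD. With no added visits the wrong sign is only chance error.

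The remedy has limits too. In a simulation with a short-lived visit effect, the week-16 path was near zero with little power. Confounding between attendance and underlying risk survives any lag. A single landmark also drops the early high-risk weeks and ignores mediator change after week 16, although SPI calls run to six months.

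All of this narrows the point. None of it supplies the missing order: no section says that mediators must precede the events they explain.

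**Conclusion.** The concern holds as a gap in specification with a documented route to bias. The outcome covers the whole year in which every post-baseline mediator is measured, section 10A sets no order, and the protocol's referral procedures link events to later care. For treatment utilization the indirect effect can take the wrong sign. Under the step 4 assumptions with baseline visits adjusted for, this happens in roughly 15% of trials at 0 added visits, about 75-98% at 1, and 98-100% at 2 or more. Without that adjustment the range is 12-69% at 1 and 47-98% at 2. For belongingness, exaggerated mediation is the likelier error.

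It should not be read as showing that events do drive visits to this degree; that is unknown. The primary between-arm comparison is unaffected, and two of the three mechanisms are exploratory. The point therefore bears on the mechanism aim only, and should be settled before that analysis is run.

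**What to change.** In section 10A, state that mediators must precede the events they explain, and prespecify one of two models:

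- **Multi-wave lagged model:** the mediator in one interval and events in the next. It keeps more of the year and uses mediator change after week 16.
- **Week-16 landmark:** visits through week 16, INQ-12 and coping at week 16, and events after week 16.

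Either should adjust for the baseline mediator, events before the mediator window, and baseline risk covariates. Label any same-period model as descriptive, and state that mediator-outcome confounding may remain. In section 10B, restate the mediation power for the lagged analysis by simulation rather than from the present formula.

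The change is one of wording and uses data already scheduled for collection. Its cost is precision: under the landmark, events in the first 31% of the year leave the mediation outcome, and power for the lagged path is low. A null lagged result would therefore be weak evidence against a mechanism.

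### The planned bootstrap 95% interval around the cost-effectiveness ratio has no sign convention for ΔE and no quadrant rule, and ΔE is close enough to zero that the interval may mislead

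*Combined protocol and SAP*

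**What the plan says.** Everything at issue is in the cost-effectiveness paragraph of Section 10A. The ratio is ΔC/ΔE, where ΔC "is the difference in costs between SPI + SOC and SOC alone" and ΔE "is the difference in the outcome measure". The primary effectiveness measure is a count of unwanted events: suicide-related hospitalizations plus medically treated and fatal suicide acts. QALYs are secondary.

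For uncertainty the plan says "Using the Crystal Ball add-in to Excel, we will bootstrap 95% confidence intervals around the CE ratio" and, in the same sentence, "and calculate a cost-effectiveness acceptability curve".

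On the direction of cost, the paragraph allows for a saving: "If direct cost savings exceed the program costs, the program is said to offer net cost savings". The mechanisms paragraph of the same section hypothesises that "SPI + SOC will result in more treatment utilization", which would raise cost. Section 9 sets provider and training costs beside the cost of inpatient, ED and outpatient care. No unit cost, cost SD, expected cost difference or expected QALY difference is given.

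The plan does not say whether ΔE is events averted or the raw event difference, how replicates in different quadrants are ordered or reported, or whether the cost-effectiveness plane or a net-benefit estimate will be shown.

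**The concern.** A percentile interval for a ratio makes sense only if a larger ratio always means a worse result. That fails once replicates have ΔE on both sides of zero. With ΔE coded as events averted, a negative ratio can then mean cheaper and better (dominant) or dearer and worse (dominated). As ΔE passes through zero the ratio also jumps from very large in one direction to very large in the other. Sorting such values and taking the 2.5th and 97.5th percentiles yields two numbers, but not a range of plausible value for money.

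The missing sign convention adds to this. If ΔE is the raw difference in events, SPI + SOC minus SOC, then dominant is negative over negative and dominated is positive over positive. Both are positive, so the sign of the ratio separates different cases from those above.

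Cost-effectiveness is a stated objective (Précis; Section 2), and the plan regards it as important for uptake by re-entry services. The ratio interval is the only interval the plan promises for it.

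**Working it through.** **1. The plan's own figure.** Section 10B gives control rates of 10% (attempts), 18% (behaviors) and 12% (hospitalizations), SPI rates of 5.5%, 9% and 7%, and a correlation of 0.50. With 78% of 800 evaluable, 0.78 × 800 = 624, or 312 per arm at 1:1 allocation. Simulating three correlated binary outcomes (latent normal, correlation 0.50), summing them and testing two-sided at 5% gives power of 95.5% by ordinal logistic regression (1001 replications) and 95.4% by the rank score test (4000 replications). The plan states 96.5%. If 0.50 is read as the correlation of the binaries themselves, power is 92.4%. The inputs are therefore being read about as intended.

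**2. Distance of the primary economic effect from zero.** The documents give no rate of medically treated or fatal acts, so let f be the share of attempts that qualify (assumed 0 to 1) and φ the correlation of the two components (assumed 0.2 to 0.5). The planning rates are cumulative incidences, so each component counts at most once per person. With h the hospitalization rate and a = f × the attempt rate:

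- ΔE (events averted per person) = (0.12 − 0.07) + f(0.10 − 0.055)
- V per arm = h(1−h) + a(1−a) + 2φ√[h(1−h)a(1−a)]
- SE = √[(V_SOC + V_SPI)/312], and zE = ΔE/SE

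In large samples more than 2.5% of replicates have ΔE < 0 when the observed zE is below 1.96. The chance of that is Φ(1.96 − zE).

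| f | φ | ΔE | SE | zE | Chance |
|---|---|---|---|---|---|
| 0 | any | 0.050 | 0.0234 | 2.14 | 43% |
| 0.25 | 0.2 | 0.061 | 0.0278 | 2.20 | 40% |
| 0.25 | 0.5 | 0.061 | 0.0304 | 2.01 | 48% |
| 0.5 | 0.2 | 0.0725 | 0.0305 | 2.38 | 34% |
| 0.5 | 0.5 | 0.0725 | 0.0338 | 2.14 | 43% |
| 1 | 0.2 | 0.095 | 0.0347 | 2.74 | 22% |
| 1 | 0.5 | 0.095 | 0.0387 | 2.45 | 31% |

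For the row with f = 1 and φ = 0.2, V_SOC = 0.2346 and V_SPI = 0.1403. Then SE = √(0.3749/312) = 0.0347 and zE = 0.095/0.0347 = 2.74. When the observed zE is below 1.96, a 95% Fieller interval for the ratio is also unbounded.

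**3. A smaller effect.** Section 10B also gives the SPI rates detectable with 80% power, among them 6.5% for attempts and 8% for hospitalizations. In the same formulas these put zE between 1.56 (f = 0.25, φ = 0.5: 0.04875/0.0312) and 2.11 (f = 1, φ = 0.2: 0.075/0.0356). The chance rises to between 44% and 66%.

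**4. How often both dominant and dominated replicates matter.** This needs a cost assumption. Let zC be the true cost difference in SE units (assumed −2 to 2) and r the correlation of the cost and effect differences (assumed 0 or −0.4). For each simulated trial with observed values c and e in SE units, the dominant share is Φ(−c) − Φ₂(−c, −e; r) and the dominated share is Φ(−e) − Φ₂(−c, −e; r), where Φ₂ is the bivariate normal distribution function. Percentage of trials in which both shares exceed 2.5%:

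| zE | r | zC −2 | −1 | 0 | 1 | 2 |
|---|---|---|---|---|---|---|
| 2.0 | 0 | 6 | 17 | 30 | 33 | 21 |
| 2.0 | −0.4 | 16 | 32 | 40 | 34 | 17 |
| 2.7 | 0 | 2 | 6 | 12 | 15 | 9 |
| 2.7 | −0.4 | 7 | 15 | 19 | 15 | 7 |

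The range is about 2% to 40%.

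**5. QALYs.** With no expected difference or SD in the documents, nothing can be computed for the second ratio.

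**The case against.** The strongest reply is that an open sign for ΔC does no harm by itself. If ΔC crosses zero while ΔE stays clearly positive, every negative ratio means dominant, and the interval runs readably from a saving to a cost per event averted. With ΔC centred on zero, the dominated share of negative ratios is about 16–21% at an observed zE of 1, 2.5–4.4% at 1.96 and 0.6–1.2% at 2.5. This stands: the trouble comes from ΔE, and it depends on the effect observed. One qualification is that among dominant replicates, averting more events for the same saving moves the ratio towards zero, so negative ratios are not ordered by value even there.

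The second reply is the acceptability curve. Built from joint replicates, it stays valid across quadrants and gives the probability that SPI is worth its cost at each threshold. That is a real mitigant. It does not supply an estimate with an interval.

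Three stronger readings are tempting, and the documents do not support them.

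- A reader might infer that the cost difference is expected to straddle zero and that the interval will therefore be uninterpretable. The sentence on net savings is conditional, and no cost figure supports a forecast.
- A reader might count trials in which any two quadrants each hold more than 2.5% of replicates. That gives 55–98% under the assumptions in step 4, but most of those trials only span ΔC = 0 with ΔE positive.
- A reader might take the named spreadsheet add-in, together with "We describe our statistical plan for determining mean change in and standard deviations of these measures above", to mean that cost and effect are drawn separately. The plan says bootstrap and does not say how the draws are made.

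**Conclusion.** The point holds in a limited form. The plan commits to an interval on ΔC/ΔE without defining the sign of ΔE or saying what happens when replicates cross quadrants. At its own planning rates ΔE for the primary economic measure is about 2.0 to 2.7 standard errors from zero, so there is roughly a 22–48% chance that the interval loses its ordering. Dominant and dominated replicates would both be present in material numbers in roughly 2–40% of trials.

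The first range rests on the assumed share of treated attempts (0 to 1), the assumed component correlation (0.2 to 0.5) and a normal approximation. The second also rests on an assumed cost difference and on an assumed cost–effect correlation of 0 or −0.4. It is a minor point, confined to the economic analysis.

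**What to change.** Amend the cost-effectiveness paragraph of Section 10A as follows.

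- Define ΔE as events averted for the primary measure and QALYs gained for the secondary one.
- Resample whole participants, cost and effect together, within arm.
- Report incremental net benefit, λΔE − ΔC, with a 95% interval at values of λ stated in advance, per event averted and per QALY. It is linear in both differences, so its percentiles are ordered by value in every quadrant.
- Show the cost-effectiveness plane with the share of replicates in each quadrant, beside the acceptability curve already planned.
- Report a ratio interval only when ΔE is clearly away from zero and essentially all replicates lie in one quadrant. State the criterion before the data are analysed by arm.

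The cost is a paragraph of plan text, a little more analysis work, and the need to commit to willingness-to-pay values, which the current plan does not give. No additional data are needed.
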